### Dose Rationale

Pirfenidone 2403 mg/d was the dose evaluated in the CAPACITY-004, CAPACITY-006, and ASCEND trials, which demonstrated favorable efficacy, and safety results compared with placebo.

## **Selection of Study Population**

The study population consists of male and female FHP patients aged 18 to 80 years (inclusive) who meet the inclusion and exclusion criteria outlined below.

## **INCLUSION CRITERIA**

Patients must fulfill all of the following criteria to be eligible for enrollment in the study:

### *Multidisciplinary Consensus Diagnosis of FHP\**

- a. Diagnosis of FHP (**figure**), defined from the first instance in which a patient was informed of having FHP for at least 3 to 6 months.
- b. Age 18 through 80 years at randomization.
- c. Diagnosis of typical or compatible FHP by HRCT according to pre-specified criteria  
(Note: HRCT scan performed within 4 months of the start of screening may be used if it meets image acquisition guidelines):
  - a. Typical FHP: Evidence of lung fibrosis (reticular abnormality and/or, traction bronchiectasis and/or, architectural distortion, and/or honeycombing) with either of the following:
    - i. Profuse poorly defined centrilobular nodules of ground-glass opacity affecting all lung zones.
    - ii. Inspiratory mosaic attenuation with three-density sign.  
AND
    - iii. Lack of features suggesting an alternative diagnosis.

These patients are required to have an identifiable antigen exposure, or an indeterminate or unidentifiable antigen exposure and BAL lymphocytosis ( $\geq 20\%$ ) or transbronchial biopsies demonstrating non-necrotizing granuloma(s) or lymphocytosis, or surgical lung histology consistent with HP.

- b. Compatible FHP: Evidence of lung fibrosis (as above) with any of the following:
  - i. Patchy or diffuse ground-glass opacity.
  - ii. Patchy, non-profuse centrilobular nodules of ground-glass attenuation
  - iii. Mosaic attenuation and lobular air-trapping that do not meet criteria for typical fibrotic HP.  
AND
  - iv. Lack of features suggesting an alternative diagnosis.

These patients are required to have an identifiable or indeterminate antigen exposure and BAL lymphocytosis ( $\geq 20\%$ ) or transbronchial biopsies demonstrating non-necrotizing granuloma(s) or lymphocytosis, or surgical lung histology consistent with HP. Otherwise, surgical lung histology consistent with HP.

c. Indeterminate FHP: CT signs of fibrosis without other features suggestive of HP and lack of features suggesting an alternative diagnosis. These patients are required to have a known antigen exposure and BAL lymphocytosis ( $\geq 20\%$ ) or transbronchial biopsies demonstrating non-necrotizing granuloma(s) or lymphocytosis, or surgical lung histology consistent with HP.

[figure not shown]
*FHP Disease Severity and Progression*

4. FVC  $\geq 40\%$ , DLCO  $\geq 30\%$  based either on historical pulmonary function tests obtained within the 60 days prior to Day 1
5. In the investigator's opinion, evidence of disease progression: worsening respiratory symptoms and an increased in extent of fibrosis on HRCT or relative decline in the FVC% of at least 5% over 24 months.
6. Able to walk  $\geq 100$  m during the 6-minute walk test (6MWT) at Screening.

*Informed Consent and Protocol Adherence*

7. Able to understand and sign a written informed consent form.
8. Able to understand the importance of adherence to study treatment and the study protocol and willing to follow all study requirements, including the concomitant medication restrictions, throughout the study

*Eligibility criteria summary (multidisciplinary discussion):*

**\*HP Diagnosis - Multidisciplinary Adjudication Committee:** the multidisciplinary discussion will be performed at the weekly NJH ILD conference attended by seven pulmonologists, one radiologist, and one pathologist. During the conference, the

exposure history (identified, indeterminate [evidence is suggestive of an association], or unidentified inciting antigen exposure), clinical details and radiologic and pathologic images will be presented. The expert chest radiologist and the expert pathologist will interpret the radiological and histological features. The final multidisciplinary diagnosis adjudication will be documented on a case report form. Differences of opinion regarding diagnostic eligibility will be resolved through consensus adjudication.

Patients with a provisional low-confidence diagnosis or HP unlikely may require surgical lung biopsy HP histology data for inclusion as determined by the adjudication committee.

## **EXCLUSION CRITERIA**

Patients with any of the following will be excluded from the study:

### *Disease-Related Exclusions*

1. Not a suitable candidate for enrollment or unlikely to comply with the requirements of this study, in the opinion of the investigator
2. Cigarette smoking at Screening or unwilling to avoid tobacco products throughout the study
3. Known explanation for the interstitial lung disease, including but not limited to radiation, drug toxicity, sarcoidosis, pneumoconiosis.
4. Clinical diagnosis of any connective tissue disease, including but not limited to scleroderma, polymyositis/dermatomyositis, and rheumatoid arthritis.
5. Expected to receive a lung transplant within 6 to 12 months from randomization or on a lung transplant waiting list at randomization.
6. The investigator judges that there has been sustained improvement in the severity of FHP during the 6-12 months prior to Screening Visit 1, based on changes in %FVC, %DLCO, and/or HRCT scans of the chest.

### *Medical Exclusions*

7. Any condition other than FHP that, in the opinion of the investigator, is likely to result in the death of the patient within 6 to 12 months.
8. Any condition that, in the opinion of the investigator, might be significantly exacerbated by the known side effects associated with the administration of pirfenidone.
9. Pregnancy or lactation. Women of childbearing capacity are required to have a negative serum pregnancy test before treatment and must agree to maintain highly effective contraception by practicing abstinence or by using at least two methods of birth control from the date of consent through the end of the study. If abstinence is not practiced, one of the two methods of birth control should be an oral contraceptive (e.g., oral contraceptive and a spermicide).
10. History of ongoing alcohol or substance abuse.

11. History of severe hepatic impairment or end-stage liver disease.
12. History of end-stage renal disease requiring dialysis.
13. Clinical evidence of active infection including, but not limited to, bronchitis, pneumonia, sinusitis, or urinary tract infection.
14. Unstable or deteriorating cardiac disease, including but not limited to the following:
  - a. Unstable angina pectoris or myocardial infarction.
  - b. Congestive heart failure requiring hospitalization.
  - c. Uncontrolled clinically significant arrhythmias.

#### *Laboratory Exclusions*

15. Any of the following liver function test criteria above specified limits: total bilirubin > 2.0 mg/dL, excluding patients with Gilbert's syndrome; aspartate or alanine aminotransferase (AST/SGOT or ALT/SGPT) >3 ULN; alkaline phosphatase >2.5 ULN within past 30 days.
16. Creatinine clearance (CrCl) <30 mL/min, calculated using the Cockcroft-Gault formula within past 30 days.
17. Electrocardiogram (ECG) with a QTc interval >500 msec at Screening.

#### *Medication Exclusions*

18. Prior use of pirfenidone, nintadinib or known hypersensitivity to any of the components of study treatment.
19. Introduction, increase or escalation of immunosuppressive pharmacological therapy within 1 month (e.g. prednisone, azathioprine, mycophenolic acid and mycophenolate mofetil).
20. Use of any of the following therapies within 28 days before Screening:
  - a. Bosentan, ambrisentan, cyclophosphamide, cyclosporine, etanercept, iloprost, infliximab, methotrexate, tacrolimus, tetrathiomolybdate, TNF- $\alpha$  inhibitors, imatinib mesylate, Interferon gamma-1b, and tyrosine kinase inhibitors.
  - b. Fluvoxamine.
  - c. Sildenafil (daily use). Note: intermittent use for erectile dysfunction is allowed.

#### **Treatments**

Study treatment is defined as either pirfenidone 2403 mg/d or placebo equivalent administered in divided doses three times per day (TID) with food. Study treatment will be titrated over 4 weeks to the full maintenance dose of 9 capsules per day (three 267-mg capsules taken orally TID with food). Subjects will remain on a stable maintenance dose for the duration of the treatment period unless the dose is reduced to manage an AE or titrated again when restarting study treatment after a 28-day or greater lapse in treatment.

#### **Missed Doses**

If subjects miss a scheduled dose, that dose should be skipped. Regular dosing should

resume with the next scheduled dose. Subjects should not take any extra doses to make up for missed doses.

### **Study Treatment Supply**

Genentech will supply all study treatment. Pirfenidone 267-mg and placebo will be supplied in opaque, hard, white gelatin capsules that are visually indistinguishable.

### **RANDOMIZATION AND BLINDING**

This is a randomized, double-blind, placebo-controlled study. Neither study personnel nor the subjects will know which study treatment the subject is receiving. Subjects will be randomized in a 2:1 ratio to receive either pirfenidone 2403 mg/d or a placebo equivalent. The placebo will be visually similar to pirfenidone. The National Jewish Health statistician will hold the randomization schedule and the clinical research unit will keep the unidentified placebo or drug bottles for each patient prepared by Genentech. On the Day 1 visit, each subject will receive his or her first bottle of assigned unidentified drug.

### **Unblinding**

Individual subject treatment assignments will not be unblinded during the study unless a subject safety issue arises in which unblinding is necessary to ensure optimal subject management. Once the study is complete, and the final analysis completed, treatment assignments will be unblinded for all subjects.

### **Study Treatment Accountability**

The monitoring of the inventory of study treatment supplies will be delegated to the National Jewish Health clinical research unit. Study treatment may not be used for any purpose other than that described in the protocol. All study treatment will be stored in a secure drug storage room with access restricted to authorized personnel. Subjects will be asked to return all used and unused bottles of study treatment at every visit. All bottles of study treatment will be recorded in a Drug Accountability Log. The study coordinator at the National Jewish Health clinical research unit will account for all study treatment received, dispensed to the subjects, returned by the subjects, not used, and sent for destruction. All documentation of study treatment shipments will be retained at the National Jewish Health Clinical Research Unit.

### **Dispensing of Study Treatment**

Study treatment will be dispensed to the subjects every 13 weeks, but may be dispensed at other visits, as needed. Subjects will be instructed to store study treatment at room temperature. Subjects will be instructed to use study treatments in the order in which they are dispensed and that they must return all used and unused study treatment bottles at every visit. Study drug returned at week 5 will be counted for compliance and returned to

the subject at those visits.

### **Concomitant Medications**

All of the following are considered concomitant medications, and data regarding their use will be collected and recorded:

1. Prescription drugs
2. Over-the-counter drugs, including vitamins, antacids, herbal and dietary supplements
3. Permitted FHP therapies: prednisone, azathioprine, mycophenolic acid and mycophenolate mofetil
4. Excluded therapies (see exclusion criteria)

### **Early Discontinuation of Study Treatment**

Study treatment will be discontinued for any of the following reasons:

1. Unacceptable toxicity (this may include serious adverse events [SAEs] related to study treatment)
2. Patient request or withdrawal of consent
3. Pregnancy
4. Investigator discretion
5. Lung transplantation

Subjects who discontinue study treatment will be asked to complete all scheduled study assessments and procedures through Week 52.

## **STUDY ENDPOINTS**

### *Primary Efficacy Outcome Variables:*

Mean change in %FVC at week 52.

### *Key Secondary Efficacy Outcome Variables*

1. Progression-free survival (PFS) defined as the time from study treatment randomization to the first occurrence of any of the following events:
  - a. Relative decline from baseline in  $\geq 10\%$  in FVC and/or DLCO
  - b. Acute exacerbation of FHP defined as acute respiratory declined leading to hospitalization or ER or Urgent care evaluation; or evidence of all of the following criteria within a 4-week period in the outpatient setting:
    - i. Increase from baseline  $\text{FIO}_2 \geq 1 \text{ L O}_2$ .
    - ii. Clinically significant worsening of dyspnea and/or cough.
    - iii. New, superimposed ground-glass opacities or consolidation or new alveolar opacities on chest x-ray or CT.
    - iv. Primary: if all other causes excluded (e.g., acute gastro-esophageal aspiration, pneumothorax, infection, left heart failure, pulmonary

embolism, or identifiable cause of acute lung injury).

- c. A decrease from baseline of at least 50 meters in 6-minute walk distance.
- d. Change in background therapy (need for a new course of PO or IV steroids or for the patient receiving maintenance prednisone, as a need to increase the dose by 10 mg or more; and/or addition of cyclophosphamide, azathioprine, mycophenolate mofetil or mycophenolic acid).
- e. Death

2. Slope of FVC over 52-week treatment period.
3. Mean change in %DLCO at week 52
4. Proportion of patients with all-cause mortality.
5. Proportion of patients with all-cause hospitalization.
6. Proportion of patients with hospitalization for respiratory cause.
7. Proportion of patients with respiratory exacerbations requiring hospitalizations.
8. Proportion of patients with evidence of progression in fibrosis on visual comparison of baseline and week 52 HRCT scans.

*Exploratory Outcome Variables:*

1. Mean change from baseline in health-related quality of life, measured by St. George's Respiratory Questionnaire (SGRQ) (3 domain scores and total score), at Week 52.
2. Mean change from baseline in health-related quality of life, measured by A Tool to Assess Quality of Life Questionnaire (L-IPF) at Week 52.
3. Mean change from Baseline to Week 52 in dyspnea as measured by the University of California at San Diego Shortness-of-Breath Questionnaire (UCSD SOBQ) score.
4. Proportion of patients with evidence of progression, stability or improvement in fibrosis on texture-based quantitative analysis of CT.
5. Candidate biomarker expression in the peripheral blood of patients with HP over the 52-study follow-up period.

*Safety Outcome Measures:*

1. Proportion of patients with treatment-emergent adverse events (AEs)
2. Proportion of patients with treatment-emergent serious adverse events (SAEs)
3. Proportion of patients with treatment-emergent adverse drug reaction (ADRs)
4. Proportion of patients with treatment-emergent serious drug reaction (SDRs)
5. Proportion of patients with AEs leading to early discontinuation of study treatment
6. Proportion of patients with treatment-emergent deaths
7. Proportion of patients with treatment-emergent changes in clinical laboratory findings, vital signs and ECGs.

## **STUDY ASSESSMENTS**

Patients will be screened for study inclusion over a period of up to 4 weeks. If eligible, subjects will receive study drug starting on Day 1 (clinic visit). Subjects will have a telephone assessment at Week 1 and 3 and in-clinic assessments on week 5, 13, 26, 39, and 52. Study assessments will include laboratory tests, spirometry, DLCO, 6MWT and Borg Scale, ECG, HRCT scan, patient reported outcome questionnaires, vital signs, height, weight, oxygen saturation and fraction of inspired oxygen (FiO2), directed history, physical examination and any changes to existing treatment regimens. Subjects will complete an AE and dosing compliance diary between all visits. Subjects who undergo lung transplantation or who chose to withdraw from study procedures early will be followed for vital status until Week 52.

### **Routine Clinical Laboratory Tests**

The following assessments will be performed at the National Jewish Health Advanced Diagnostic Laboratories:

1. Hematology (complete blood count with platelet count and automated differential)
2. Serum chemistry profile
3. Pregnancy test for women of childbearing capacity

### **Biomarkers in blood**

The study will include a significant exploratory component focused on identification of biomarkers that may be prognostic for patients likely to have an accelerated rate of disease progression or diagnostic for identifying patients likely to benefit from treatment. Certain biomarkers may be differentially expressed in FHP and may change as a result of pirfenidone treatment. The blood samples that will be obtained for this study may help identify these biomarkers. Serum and plasma samples will be collected at baseline and at week 52 to assess the relationship between FHP related biomarkers (identified by RNA-seq and ChIP-seq), disease progression, clinical status, and treatment benefit. We hypothesize that distinct peripheral blood mononuclear cells gene expression profiles have the potential to be an adjunct to the traditional clinical-radiologic-pathologic assessment, in providing disease-specific prognostic information and help identify novel pathways for targeted therapy.

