#### **Before Randomization**

1. Directed history (including review of AEs/SAEs, concomitant medications, oxygen use, and hospitalizations).
2. Physical examination, vital signs, FiO2 and weight.
3. Clinical laboratory assessments, including hematology, serum chemistries, pregnancy test for women of childbearing capacity.
4. Spirometry (FVC, FEV1) and DLCO.
5. 6MWT with Borg Scale pre and post.

6. UCSD SOBQ, L-IPF and SGRQ.
7. Confirmation of patient eligibility for study participation.
8. Genetic testing (RNA-seq and ChIP-seq).

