### **Exploratory Outcome Variables**

Questionnaire-based outcomes comparing Baseline to 52 weeks will be analyzed using a linear regression model with a separate intercept for each subject, a dichotomous time-point effect, and a multiplicative interaction between time-point and treatment.

Changes in texture-based quantitative analysis of CT progression of fibrosis will be analyzed using multinomial regression with a separate intercept for each subject, a dichotomous time-point effect, and a multiplicative interaction between time-point and treatment.

Statistical analyses of RNA-seq and ChIP-seq results from PBMC samples will be performed with the DESeq2 package in the R language. The p-values of Wald tests for differential expression will be adjusted using the Benjamini-Hochberg false discovery rate procedure to account for multiple testing after filtering out genes with mean normalized counts below a threshold. Significantly differentially expressed genes will be assigned to biochemical pathways and functional categories using KEGG and Gene Ontology databases using tools including GATHER, DAVID, R packages such as KEGGprofile and topGO, as well as Ingenuity pathway analysis. Diversity of immune cell types will be derived from the gene expression profiles of each sample to ensure valid comparisons and modeling. Expression profiles (baseline and week 52) will be correlated within the two HP arms using an ANOVA analysis.

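### The protocol names only serum and plasma as biomarker specimens, while the RNA-seq and ChIP-seq analyses need PBMCs, whose collection is nowhere specified

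*Combined protocol and SAP*

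**What the plan says.** **What is collected.** Study Assessments, Biomarkers in blood, is the only place that names a specimen for the biomarker work: "Serum and plasma samples will be collected at baseline and at week 52 to assess the relationship between FHP related biomarkers". The sentence continues "identified by RNA-seq and ChIP-seq), disease progression, clinical status, and treatment benefit", so the two assays and the two specimens appear together. The sentence before it is generic: "The blood samples that will be obtained for this study may help identify these biomarkers".

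**What is hypothesised.** The sentence that follows moves to cells: "We hypothesize that distinct peripheral blood mononuclear cells gene expression profiles have the potential to be an adjunct".

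**What is scheduled.** The Day 1 list (Before Randomization, item 8) has an entry beginning "Genetic testing (RNA-seq and ChIP-seq", and the Week 52 list repeats it as item 12. Week 52 item 4 also mentions genetic testing, among the clinical laboratory assessments. None of these entries gives a specimen, tube, volume or processing step.

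**What is analysed.** Statistical Methods, Exploratory Outcome Variables, says: "Statistical analyses of RNA-seq and ChIP-seq results from PBMC samples will be performed with the DESeq2 package in the R language". It adds: "Diversity of immune cell types will be derived from the gene expression profiles of each sample".

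**Which endpoint this serves.** Study Endpoints, exploratory outcome 5, is "Candidate biomarker expression in the peripheral blood of patients with HP over the 52-study follow-up period". It names no blood fraction.

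**The concern.** The collection text and the analysis text describe different materials. Serum and plasma are what remains of blood once the cells have been removed. PBMC expression profiles require the cells, ChIP-seq requires chromatin from them, and an estimate of immune cell composition presupposes a cellular sample. Staff who worked from the collection sentence alone would keep the fractions that the analysis does not use and discard the one that it does.

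The timing makes this worth correcting. The section Eligibility and Randomization (Day 1) puts all Day 1 procedures before randomisation and before the first dose, and no biomarker sample is scheduled during Screening. Day 1 is therefore the only scheduled pre-treatment biomarker sample. If cells are not isolated then, that patient has no baseline profile. The planned comparison of baseline and Week 52 profiles within the arms would then be lost for that patient, and so would any use of baseline expression to predict progression or benefit. The protocol describes this work as a significant exploratory component.

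**Working it through.** The plan gives no figure for this point, so the check is mainly a comparison of texts.

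**1. The sections side by side**

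| Section | Specimen named | Assay named |
|---|---|---|
| Study Endpoints, exploratory outcome 5 | Peripheral blood, no fraction | None |
| Routine Clinical Laboratory Tests | Hematology, serum chemistry and pregnancy test only | None for biomarkers |
| Biomarkers in blood, collection sentence | Serum and plasma | RNA-seq, ChIP-seq |
| Biomarkers in blood, hypothesis | PBMC | Gene expression |
| Day 1, item 8 | None | RNA-seq, ChIP-seq |
| Week 52, item 4 | None | Genetic testing, not specified |
| Week 52, item 12 | None | RNA-seq, ChIP-seq |
| Statistical Methods, Exploratory Outcome Variables | PBMC | RNA-seq, ChIP-seq, cell-type diversity |

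**2. What the comparison shows.** Serum and plasma are the only specimens named for collection. PBMC is the only specimen named for analysis. No section links the two by providing for whole blood to be drawn and cells isolated or stored. In the other direction, no analysis in the Statistical Methods uses a serum or plasma biomarker, and no analyte is named for either.

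**3. Could the named specimens serve the named analysis?** No. Whatever cell-free nucleic acid might be recovered from plasma, it is not a PBMC sample, so it does not meet the analysis plan as written.

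**4. Number of samples exposed.** The inputs are about 42 randomised subjects and 10% attrition (Sample Size and Power Considerations), and two sampling visits (Biomarkers in blood).

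- Ceiling, with no attrition: 42 x 2 = 84 patient-visit samples.
- Subjects remaining at Week 52: 42 x 0.90 = 37.8, about 38. This agrees with the plan's own 13 + 25 = 38.
- With that attrition: 42 (Day 1) + 38 (Week 52) = 80 samples.
- Of these, complete pairs: 38 patients, or 38 x 2 = 76 samples.

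Applying the 10% to Week 52 blood samples is an assumption. The plan states it for the sample size of the primary comparison.

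**The case against.** **PBMC collection is plainly intended.** The hypothesis and the analysis section both name PBMCs, and the Day 1 and Week 52 lists schedule the two assays in their own right, without tying them to serum or plasma. This is largely right. A reader might infer that the sequencing data cannot be obtained at all, and the documents do not support that. They show that the collection line does not match the evident intent.

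**Serum and plasma may have a different purpose.** The phrase about RNA-seq and ChIP-seq can be read as describing the biomarkers and not the samples, so that serum and plasma would be used to measure candidates that sequencing has identified. That reading is available. It means one cannot conclude that serum and plasma are the wrong specimens or should be dropped. It leaves PBMC collection just as unspecified, and it leaves the serum and plasma measurements without a named analyte or analysis.

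**A laboratory manual may cover it.** Tubes, isolation and preservation are details that such a manual could hold. None is included or cited for this purpose, so this can be neither confirmed nor excluded. A manual calling for PBMCs would still differ from the protocol's collection sentence.

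**It is only exploratory.** This is correct, and it limits the weight of the point.

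**Conclusion.** The inconsistency stands. The one sentence that names biomarker specimens gives cell-free fractions, the stated analysis needs cells, and nothing else in the documents fills the gap. Followed literally, it would leave exploratory outcome 5 without the material its analysis requires, and a missed Day 1 specimen could not be replaced.

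The exposure is at most 84 patient-visit samples, or about 80 with the planned attrition. This is a ceiling that applies only if no PBMCs are drawn, which the documents do not establish. A reader might take it as a forecast that every baseline-to-Week-52 comparison will be lost. With PBMC collection probably intended, that goes too far.

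Only exploratory outcome 5 is touched. The primary, key secondary and safety analyses, the sample size and the type I error are unaffected. The point merits correction because the pre-treatment sample is unrepeatable and the change is a few words.

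**What to change.** - In Biomarkers in blood, name PBMCs isolated from whole blood as the specimen for RNA-seq and ChIP-seq, collected on Day 1 before randomisation and at Week 52.
- Use the same specimen wording in the genetic-testing entries for Day 1 (item 8) and Week 52 (items 4 and 12), and make clear whether the two Week 52 entries refer to one draw or two.
- State what the serum and plasma are for. They need not be deleted; storing them to measure candidates found later would be a sufficient purpose if the protocol says so.

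The cost is protocol wording, plus any matching laboratory instructions. Blood is already taken at both visits. The practical burden is same-day cell processing, which the analysis section already presupposes by specifying PBMC samples.
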